6.4 STUDY INTERVENTION COMPLIANCE

IMP accountability will be as described below:

- Intervention units are returned by the participant at each visit. In case of DTP process, the intervention units can be returned by the carrier (if defined in the contract)
- The Investigator will count the number of tablets remaining in the returned packs and complete the Intervention Log Form
- The Investigator will record the dosing information on the appropriate page(s) of the case report form (CRF)
- The monitor in charge of the study will then check the CRF data by comparing them with the IMP that he/she has retrieved and intervention log forms

When participants are dosed at the site, they will receive study intervention directly from the Investigator or designee, under medical supervision. The date and time of each dose administered in the clinic will be recorded in the source documents. The dose of study intervention and study participant identification will be confirmed at the time of dosing by a member of the study site staff other than the person administering the study intervention.

When participants self-administer study intervention(s) at home, compliance with study intervention will be assessed at each visit. Compliance will be assessed by counting returned tablets during the site visits and documented in the source documents and relevant form. Deviation(s) from the prescribed dosage regimen should be recorded.

A record of the quantity of SAR443820 or matching placebo dispensed to and administered by each participant must be maintained and reconciled with study intervention and compliance records. Intervention start and stop dates, including dates for intervention delays and/or dose reductions, will also be recorded.

6.5 DOSE MODIFICATION

Dose modification is not foreseen in this study. The IMP treatment may need to be interrupted or permanently discontinued if deemed necessary due to an AE.

6.6 CONTINUED ACCESS TO INTERVENTION AFTER THE END OF THE STUDY

Part B is an open-label long-term extension period up to Week 96 in which all eligible participants from Part A may rollover to Part B and receive open-label IMP. In addition to this open-label extension, poststudy access to study medication could be provided based on local/country regulations.

6.7 TREATMENT OF OVERDOSE

For this study, overdose is defined as at least at least █ mg IMP within 24 hours.

The Sponsor does not recommend a specific treatment for an overdose, and treatment of an overdose will be based on the Investigator's clinical judgment in conjunction with the Sponsor's agreement.

In the event of an overdose, the Investigator should:

- Closely monitor the participant for any AE/SAE and laboratory abnormalities until the IMP can no longer be detected systemically (at least 2 days). Provide supportive and symptomatic treatment as needed.
- Obtain a plasma sample for PK analysis as soon as possible from the date of the last dose of study intervention.
- Evaluate the participant to determine whether study intervention should be interrupted or whether the dose should be reduced.
- Document appropriately in the CRF.
- Contact the Sponsor immediately.

6.8 CONCOMITANT THERAPY

Any medication or vaccine (including over-the-counter or prescription medicines, recreational drugs, vitamins, and/or herbal supplements) that the participant is receiving at the time of enrollment or receives during the study must be recorded along with the following:

- Reason for use
- Dates of administration including start and end dates
- Dosage information including dose and frequency
- The use of any live vaccine is prohibited within 14 days before the Screening Visit and during study duration.

The Sponsor should be contacted if there are any questions regarding concomitant or prior therapy.

The concomitant therapy should be reported to the Investigator and recorded on the Concomitant Medications electronic case report form (eCRF). The reported medications will be reviewed and evaluated by the Investigator or designee to determine whether they affect a participant's eligibility to participate or continue to participate in the study.

Medications for treatment of MS symptoms (eg, walking impairment, fatigue, spasticity, incontinence, pain) should be maintained at a stable dose prior to screening and for the duration of the treatment period (except those per exclusion criterion [E 11](#)), if clinically feasible. Allowed concomitant DMTs (ie, interferons, glatiramer acetate, fumarates, and teriflunomide) should be maintained at the pre-enrollment dose. Prohibited medications listed in exclusion criteria may not be exhaustive, and any exceptions (eg, newly marketed DMTs during the course of the study) should be discussed with the Medical Monitor.

Participants must abstain from starting prescription or nonprescription drugs (including vitamins, recreational drugs, and dietary or herbal supplements) within 7 days (or 14 days if the drug is a potential enzyme inducer) or 5 half-lives (whichever is longer) before the start of study intervention until completion of the follow-up visit, unless, in the opinion of the Investigator and Sponsor, the medication will not interfere with the study.

Based on in vitro results, SAR443820 is mainly metabolized by CYP3A4. A [REDACTED] in [REDACTED] was observed in the presence of [REDACTED] in a drug-drug interaction study. Based on PBPK modeling, administration of potent CYP3A4 inhibitors are [REDACTED]. Administration of strong CYP3A4 inducer is predicted to decrease the SAR443820 AUC. Therefore, concomitant medications or substances that are strong or moderate inhibitors or strong inducers of CYP3A4 (Appendix 10, Section 10.10, [Table 9](#)) are not allowed within the specific wash out period before the Screening Visit and for the duration of Part A and Part B.

In Part A, any modifications of SOC therapy will result in participant discontinuation from the IMP. This includes stopping, changing the dose of allowed SOC DMTs, or switching to another allowed SOC DMT, or switching to a prohibited DMT (per exclusion criterion [E 12](#)). In Part B, changes to dose of allowed DMTs or switching to another allowed DMT will be permitted.

The use of any live vaccine is prohibited within 14 days before the Screening Visit and during study duration.

6.8.1 Rescue medicine

For all participants that experience relapse in the case of MS relapse, rescue treatments are allowed as per local routine practice (eg, high dose intravenous methylprednisolone for 3 to 5 days). Rescue treatments are defined as limited to this prescribed timeframe and medication and does not include transition to new permanent DMTs whether participants are switched to another allowed DMT or any prohibited DMT. Rescue medications must be reported in the eCRF, as for all other concomitant medications. The Investigator should document the discussion with the participant and the decision for rescue treatment in the source documentation.

7 DISCONTINUATION OF STUDY INTERVENTION AND PARTICIPANT DISCONTINUATION/WITHDRAWAL

Discontinuation of specific sites or of the study as a whole are detailed in Appendix 1 ([Section 10.1](#)).

7.1 DISCONTINUATION OF STUDY INTERVENTION

7.1.1 Permanent discontinuation

Compliance with and continuation of the study intervention is encouraged, while maintaining the safety of study participants and integrity of the study. In certain instances, it may be medically necessary for a participant to permanently discontinue study intervention.

In case of the events listed below, permanent discontinuation of the IMP is mandatory (this list is not intended to be exclusive):

- The Investigator or Sponsor determines it is in the best interest of the participant.
- Occurrence of AEs or any other medical condition that, in the opinion of the Investigator or Sponsor, may jeopardize the participant's safety or data integrity. These include, but are not limited to, abnormal livers tests and meeting the stopping criteria.
- Noncompliance with the protocol, dosing regimen and visits including switching DMT or taking a prohibited DMT in Part A or Part B.
- Pregnancy of a female participant.
- Occurrence of convulsions.

Any abnormal laboratory value or ECG parameter will be immediately rechecked for confirmation after 24 hours before making a decision regarding permanent discontinuation of the IMP for the concerned participant.

Handling of participants after permanent intervention discontinuation

If a participant is withdrawn from study intervention permanently, the Sponsor will be notified within 2 business days and the date and reason(s) for the withdrawal will be documented by the Investigator in the appropriate pages of the eCRF when considered as confirmed.

Participants will be followed up according to the study procedures specified in this protocol up to study completion, or up to recovery or stabilization of any AE to be followed up as specified in this protocol, whichever comes last.

If possible, and after the definitive discontinuation of intervention, the participants will be assessed using the procedure normally planned for the last treatment day with the IMP including a PK sample. Details are provided in the SoA ([Section 1.3](#)). All cases of definitive intervention discontinuation must be recorded by the Investigator in the appropriate pages of the eCRF when considered as confirmed.

All cases of permanent intervention discontinuation must be recorded by the Investigator in the appropriate pages of the eCRF when considered as confirmed.

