5.1 INCLUSION CRITERIA

Participants are eligible to be included in the study only if all of the following criteria apply:

Age

I 01. Participant must be 18 to 60 years (inclusive) of age, at the time of signing the informed consent.

Type of participant and disease characteristics

I 01. Participants with a diagnosis of RRMS, SPMS (relapsing or non-relapsing), or primary progressive subtype according to the 2017 revision of the McDonald diagnostic criteria (SPMS diagnostic criteria according to [13] include an initial relapsing remitting disease course followed by progression with or without occasional relapses, minor remissions, and plateaus; progression denotes the continuous worsening of neurological impairment over at least 6 months).

I 02. Participants with an Expanded Disability Status Scale score of 2-6 inclusive at screening.

I 03. Participants who are either untreated or in the opinion of the Investigator are stable on an allowed DMT (interferons, glatiramer acetate, fumarates, or teriflunomide) for at least the past 3 months, AND not anticipated to require a change in MS treatment for the duration of Part A and Part B (through Week 96); in Part B changes in dose of allowed DMTs or transition to other allowed DMTs is permitted).

Weight

I 04. Participants with body weight ≥ 45 kg and body mass index (BMI) ≥ 18.0 kg/m².

Sex, contraceptive/barrier method, and pregnancy testing requirements

I 05. All

Contraceptive use by men and women should be consistent with local regulations regarding the methods of contraception for those participating in clinical studies.

a) Male participants

- Male participants are eligible to participate if they agree to the following during the study period and for at least 92 days following their last dose of IMP:
- Refrain from donating or cryopreserving sperm
Plus, either:
- Be abstinent from heterosexual intercourse as their preferred and usual lifestyle (abstinent on a long-term and persistent basis) and agree to remain abstinent

OR

- Must agree to use contraception/barrier (male condom) as detailed below:
A male condom and an additional highly contraceptive method as described in [Section 10.4.2](#) when having sexual intercourse with a woman of childbearing potential (WOCBP) who is not currently pregnant

b) Female participants

Female participants are eligible to participate if they are not pregnant or breastfeeding and 1 of the following conditions applies:

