- E 11. Participants with a current use of any medications that are moderate or strong inhibitors or strong inducers of CYP3A4 (see Appendix 10 [[Section 10.10](#)]).
- E 12. Participants with a current use of any of the following medications/treatments: fampridine/dalfampridine, ofatumumab, fingolimod, cladribine, siponimod, ponesimod, ozanimod, alemtuzumab, mitoxantrone, ocrelizumab, natalizumab, or similar approved compounds but with different trade names and any unapproved treatments or therapies for MS; any DMTs newly approved after January 2023 that are marketed at any time during the course of the double-blind study period. These medications are not allowed within 5 half-lives before the Screening Visit and for the duration of Part A and Part B.

If the participant has received any of the prohibited medications/treatments, washout will be required according to the table below (no washout is required for permitted medications):

Medication	Exclusionary if used/used within required wash out period
Systemic corticosteroids, adrenocorticotropic hormone	4 weeks prior to the baseline MRI scan
Plasmapheresis, fingolimod, and natalizumab (participants who have discontinued natalizumab in the 24 weeks prior to randomization should be evaluated to rule out PML)	8 weeks prior to randomization
B cell depleting therapies such as ocrelizumab and rituximab	24 weeks prior to randomization or until the return of B cell counts to normal levels, whichever is longer
Alemtuzumab	4 years prior to randomization
Other prohibited MS DMT	5 half-lives or until the end of pharmacodynamics activity, whichever is longer

Abbreviations: DMT = disease-modifying therapy; MRI = magnetic resonance imaging; MS = multiple sclerosis; PML = progressive multifocal leukoencephalopathy

Prior/concurrent clinical study experience

E 13. Participants who have prior/concurrent clinical study enrollment, ie, the participant has taken other investigational drugs within 4 weeks or 5 half-lives, whichever is longer, before the first Screening Visit; concurrent or recent participation in non-interventional studies may be permitted.

Diagnostic assessments

E 14. Participants with a positive human immunodeficiency virus (HIV) antibody test.

E 15. Participants with abnormal laboratory test(s) at the Screening Visit:

- Alanine aminotransferase (ALT) or aspartate aminotransferase (AST) $>3.0 \times$ upper limit of normal (ULN)

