7.1.4 Rechallenge

Reinitiation of intervention with the IMP will be done under close and appropriate clinical and/or laboratory monitoring once the Investigator has considered according to his/her best medical judgment that the responsibility of the IMP(s) in the occurrence of the concerned event was unlikely, that there are no safety concerns, that the selection criteria for the study are still met (refer to [Section 5.1](#) and [Section 5.2](#)), and the criteria for the permanent treatment discontinuation have not been met.

For a regional or national emergency declared by a governmental agency, contingency measures are included in Appendix 9 [[Section 10.9](#)].

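### Protocol 7.1.1 orders a permanent stop of study drug for switching DMT in Part B, although 6.8 and inclusion criterion I 03 permit a switch to another allowed DMT

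*Protocol*

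**What the plan says.** Protocol 7.1.1 introduces its list with the statement that "permanent discontinuation of the IMP is mandatory" when a listed event occurs. The third bullet reads "Noncompliance with the protocol, dosing regimen and visits including switching DMT or taking a prohibited DMT in Part A or Part B".

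Protocol 6.8 treats the two parts differently. For Part A: "In Part A, any modifications of SOC therapy will result in participant discontinuation from the IMP". For Part B: "In Part B, changes to dose of allowed DMTs or switching to another allowed DMT will be permitted". Inclusion criterion I 03 (Protocol 5.1) gives the same permission: "in Part B changes in dose of allowed DMTs or transition to other allowed DMTs is permitted".

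Prohibited DMTs are dealt with separately in exclusion criterion E 12 (Protocol 5.2): "These medications are not allowed within 5 half-lives before the Screening Visit and for the duration of Part A and Part B".

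On the analysis side, SAP 3.2.2.2 restricts the Part B sNfL model to data collected up to IMP discontinuation. SAP 3.1 closes the Part B on-treatment safety period 14 days after the last dose, or at death or last contact if earlier.

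**The concern.** For a participant who moves from one allowed DMT to another during Part B, 6.8 and I 03 let treatment continue, while 7.1.1 as worded ends it permanently. Nothing in 7.1.1 points to 6.8 or says which section prevails, so two sites could handle the same switch differently.

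At stake for the participant is open-label drug withdrawn for a change the protocol allows. On the literal text this cannot be undone, because Protocol 7.1.4 makes restarting conditional on "the criteria for the permanent treatment discontinuation have not been met". At stake for the trial are the participant's later sNfL values, including the Part B principal time point, and treatment-emergent follow-up in a part of the study that has long-term safety as an objective.

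**Working it through.** No figure in the plan needs reproducing. The check is a comparison of the texts, followed by simple arithmetic on the consequence for one participant.

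**Instructions by event**

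| Event | 6.8, I 03, E 12 | 7.1.1 read literally | Consistent? |
|---|---|---|---|
| DMT switch in Part A | Discontinue IMP (6.8) | Discontinue IMP | Yes |
| Prohibited DMT, Part A or B | Not allowed (E 12) | Discontinue IMP | Yes |
| Switch to another allowed DMT, Part B | Permitted (6.8, I 03) | Discontinue IMP | **No** |
| Dose change of an allowed DMT, Part B | Permitted (6.8, I 03) | Not named | No express conflict |

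The conflict is confined to the third row.

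**Does grammar remove it?** If the closing reference to both parts governs both limbs of the bullet, switching in Part B is covered expressly. If it governs only the prohibited-DMT limb, switching carries no part limit and still reaches Part B. Neither parsing restores the 6.8 permission.

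**Consequence for one participant.** Let the literal stop fall at Week *w*, with 48 < *w* < 96. The values of *w* below are illustrative assumptions.

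- Weeks on drug lost = 96 − *w*
- Share of Part B lost = (96 − *w*)/48
- On-treatment safety period closes at *w* + 2 weeks (14 days, SAP 3.1)
- SAR443820 exposure kept, if on placebo in Part A = *w* − 48

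| Stop at Week | Weeks lost | Share of Part B lost | Safety period closes | Exposure kept if on placebo in Part A |
|---|---|---|---|---|
| 60 | 96 − 60 = 36 | 36/48 = 75% | Week 62 | 12 of 48 weeks |
| 72 | 96 − 72 = 24 | 24/48 = 50% | Week 74 | 24 of 48 weeks |
| 84 | 96 − 84 = 12 | 12/48 = 25% | Week 86 | 36 of 48 weeks |

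Without the stop, the safety period would close between Week 96 and Week 98. In all three cases the participant contributes no Week 96 sNfL value to the model. Under 6.8 the participant stays on IMP, and the most natural reading of SAP 3.2.2.2 then keeps those values, because its only stated cut-off is IMP discontinuation.

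The number of Part B switchers is not given, so neither a count nor any widening of the confidence interval can be computed.

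**The case against.** The best defence is that the bullet opens with noncompliance and that switching is only an example of it. A Part B switch that 6.8 expressly permits is not noncompliance, so the specific rule in 6.8 governs and 7.1.1 reaches only non-permitted switches. That reading leaves the switching limb some work to do. Section 6.8 itself speaks of switching to a prohibited DMT. It also says the list of prohibited medications may not be exhaustive, and E 12's clause on newly approved DMTs is tied to the double-blind period. The amendment history (Protocol 10.12.1) shows the Part B permission in the inclusion criterion and the Part B reference in this bullet arriving in the same amendment, which suggests they were meant to coexist.

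This shows that the sponsor probably did not intend to cancel the permission, and the softer reading is possible. It does not cure the text. The bullet names switching as an instance of noncompliance, lists it apart from taking a prohibited DMT, and carries no qualifier or cross-reference. The reader of a mandatory stopping rule has to infer the exception.

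The points about limited impact stand:

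- I 03 enrols only people not expected to need a treatment change through Week 96.
- Part B sNfL is descriptive.
- SAP 3.3.2 keeps secondary efficacy values collected after a change in treatment status.
- Participants who stop drug are still followed, and post-treatment adverse events are still reported.
- Section 6.8 offers a safeguard: "The Sponsor should be contacted if there are any questions regarding concomitant or prior therapy". Section 7.1.1 also requires Sponsor notification within 2 business days, although that comes after the withdrawal.

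The irreversibility point applies only on the literal reading. On the softer one, a permitted switch never meets the stopping criteria.

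**Conclusion.** The concern holds. As worded, 7.1.1 gives a mandatory instruction that contradicts 6.8 and I 03 for one foreseeable event, a Part B switch between allowed DMTs. The effect is small: it concerns only participants who make such a switch at a site that follows 7.1.1 literally, and their number is unknown. For each of them it means lost time on drug, no Week 96 sNfL in the descriptive model and an earlier close of the on-treatment safety period. The Part A primary analysis is not affected, no bias is claimed, and the SAP is not at fault. It should be corrected because it is an operative stopping rule and the correction is easy.

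**What to change.** Reword the example in the 7.1.1 bullet to: *switching DMT in Part A, or taking a prohibited DMT in Part A or Part B*. This agrees with 6.8 and I 03. A non-allowed DMT that falls outside the E 12 list remains covered by the bullet's opening reference to noncompliance with the protocol.

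The cost is one line of protocol text, subject to the usual amendment approval. No SAP change is needed. Sample size, eligibility and the planned analyses stay as they are.

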7.1.2 Liver function stopping criteria

Discontinuation of study intervention for abnormal liver tests is required by the Investigator when a participant meets one of the conditions outlined in [Section 10.6](#) or in the presence of abnormal liver chemistry test results not meeting protocol-specified stopping rules if the Investigator believes that it is in best interest of the participant.

7.1.3 Temporary discontinuation

Temporary intervention discontinuation may be considered by the Investigator because of suspected AEs or disruption of the clinical trial due to a regional or national emergency declared by a governmental agency (Appendix 9 [[Section 10.9](#)]). For all temporary intervention discontinuations, the duration should be recorded by the Investigator in the appropriate pages of the eCRF. Temporary discontinuation of study intervention is defined as stopping study intervention for a minimum of 1 day and a maximum of 2 weeks accumulative in Part A or 8 weeks accumulative in Part B.

7.1.4 Rechallenge

Reinitiation of intervention with the IMP will be done under close and appropriate clinical and/or laboratory monitoring once the Investigator has considered according to his/her best medical judgment that the responsibility of the IMP(s) in the occurrence of the concerned event was unlikely, that there are no safety concerns, that the selection criteria for the study are still met (refer to [Section 5.1](#) and [Section 5.2](#)), and the criteria for the permanent treatment discontinuation have not been met.

For a regional or national emergency declared by a governmental agency, contingency measures are included in Appendix 9 [[Section 10.9](#)].

